7.4 Baseline Visit

The following standard of care evaluations and study assessments will be performed at baseline and documented on the relevant electronic case report forms (eCRFs):

- Demographics & medical history
- Pregnancy test (urine/serum), if female with childbearing potential
- Ejection fraction
- Medication assessment (anticoagulants and antiplatelet agents only)
- Labs (GFR, troponin, CBC)
- MRI, including DWI and T2-FLAIR, conducted according to study MRI procedures; images sent to independent reader per site instructions
 - o MRI is conducted within 14 days pre-procedure
- National Institute of Health Stroke Scale (NIHSS)
- Montreal cognitive assessment (MoCA)
- Modified Rankin Scale (mRS)

After the baseline evaluations, the general inclusion and exclusion criteria should be reviewed to ensure that the subject continues to be eligible for the study.

7.5 Treatment Visit

The EmStop System will be prepared and flushed per the device Instructions for Use (IFU). A guidewire will be advanced to the ascending aorta, and the EmStop System will be loaded onto the proximal end of the guidewire for delivery and deployment within the ascending aorta. A commercially available Abbott or Medtronic transcatheter heart valve delivery catheter will be inserted through the EmStop System filter sheath, and the TAVR procedure will proceed according to standard of care. After the TAVR delivery catheter is removed, the EmStop filter will be collapsed into the in-line sheath and the EmStop System will be removed.

The assessments described below will be performed and results will be recorded on the relevant eCRFs.

- Adverse event assessment
- Device performance assessment
- Medication assessment (anticoagulants and antiplatelet agents only)
- Debris captured by the EmStop System filter will be sent for gross and histological assessment following the Pathology Core Lab Guidelines

7.6 Pre-Discharge

Unless specified otherwise below, the following assessments will be performed before discharge or 7 days post-op, whichever occurs first, and documented on the relevant eCRFs:

- Adverse event assessment
- Medication assessment (anticoagulants and antiplatelet agents only)
- MRI, including DWI and T2-FLAIR, conducted according to study MRI procedures; images sent to independent reader per site instructions
 - MRI is conducted **18-36 hours post-procedure**
- Labs (GFR, troponin, CBC)
 - Pre-discharge labs will be collected within 72 hours post-procedure
- National Institute of Health Stroke Scale (NIHSS)

7.7 30-Day [± 7 days] Follow-up Visit

The assessments described below will be performed, and results will be recorded on the relevant eCRFs.

- Adverse event assessment
- Medication assessment (anticoagulants and antiplatelet agents only)
- Labs (GFR)
- Montreal cognitive assessment (MoCA)
- Modified Rankin Scale (mRS)

At the conclusion of this follow-up visit, subjects will exit from this study via completion of the Study Completion eCRF. Subjects will continue to be followed by their physician per usual care.

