5.0 ENDPOINTS

5.1 Primary Safety Endpoint

The primary safety endpoint for the study is the occurrence of MACCE at 30 days, defined as a composite of the following VARC-2 defined components:

- All-cause mortality
- All stroke (disabling and non-disabling)
- Acute kidney injury (AKI) Stage 2 or 3 (including renal replacement therapy) within 72 hours

5.2 **Primary Performance Endpoint**

The primary performance endpoint for the study is device procedural success, defined as successful insertion, deployment, positioning, and removal of the EmStop System in the absence of device interference.

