6.5.3 General Exclusion Criteria

Subjects must not meet any of the following exclusion criteria:

- 1. Requires urgent or emergent TAVR procedure
- 2. Contraindicated to MRI
- 3. Previously implanted aortic or mitral valve bioprosthesis
- 4. Hepatic failure (Child-Pugh class C)
- 5. Hypercoagulable state that cannot be corrected by additional periprocedural heparin
- 6. Planned to undergo any other cardiac surgical or interventional procedure (e.g., concurrent coronary revascularization) during the TAVR procedure or within 30 days prior to the TAVR procedure. NOTE: Diagnostic cardiac catheterization is permitted up until baseline MRI is obtained. Once baseline MRI is obtained, no additional intra-aortic or intracardiac procedure may occur.
- 7. Acute myocardial infarction within 30 days of the planned index procedure
- 8. Renal failure, defined as estimated glomerular filtration rate (eGFR) <30 mL/min
- 9. Documented history of stroke or TIA within the prior 6 months, or any prior stroke with a permanent major disability or deficit (NIHSS >1 at baseline)
- 10. Left ventricular ejection fraction ≤30% within 3 months prior to procedure
- 11. History of intolerance, allergic reaction, or contraindication to any of the study medications, including heparin, aspirin, clopidogrel, or a sensitivity to contrast media or anesthesia that cannot be adequately pre-treated
- 12. Known allergy or sensitivity to nickel-titanium
- 13. Active endocarditis or ongoing systemic infection, defined as fever (>38°C) and/or white blood cell (WBC) >15,000 IU

- 14. Undergoing therapeutic thrombolysis
- 15. History of bleeding diathesis or a coagulopathy
- 16. Known or suspected to be pregnant, or is lactating; female subjects of child-bearing potential must have a negative serum or urine pregnancy test within 48 hours prior to the index study procedure.
- 17. Currently participating in another drug or device clinical study
- 18. Any other clinical reason, as deemed by the investigators of the study, by which the patient would not be an appropriate candidate for the study
- 19. Vulnerable subject populations (e.g., incarcerated or cognitively challenged adults)

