8.0 STATISTICAL METHODS

8.1 Analysis Data Sets

The primary analysis will consist of all available data on all subjects enrolled, referred to in ICH E9 ("Statistical Principles for Clinical Trials") as the full analysis set. As the study is a treatmentonly, single arm design, summaries of results will principally be presented for the entire study population.

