11.2 Adverse Event Collection & Documentation

Collection of adverse events will start on the day of the procedure for enrolled subjects and will be assessed and reported throughout the study. Investigators must obtain all information available to determine the seriousness, relatedness, and outcome of the adverse event and to assess whether it meets the criteria for classification as an unanticipated adverse device effect (UADE) requiring immediate notification. All adverse events will be followed until resolution or investigator determination that the subject's condition is stable.

All reported adverse events will be documented on the Adverse Event CRF. Copies of deidentified source documentation that contain significant information related to the event, such as progress notes, consultations, nurse notes, operative reports, and subject summaries may be requested by the sponsor, CRO, Medical Monitor and/or core lab as needed for evaluation and adjudication.

The following are not considered reportable adverse events for this study:

- Any normal expected postoperative complaints or symptoms unless the event involves a clinically significant change in severity or duration of symptoms or requires clinical intervention that is different from ordinary postoperative care. Expected postoperative complaints and findings include, but are not limited to headache, edema, nausea, vomiting, and postoperative pain (excluding chest pain).
- Any condition that is recorded as pre-existing at baseline, unless there is a worsening of that condition in terms of nature, severity, or degree of incidence.
- Planned hospitalization for pre-existing conditions or a procedure required by the protocol, without serious deterioration in health.

In case of subject death, it is requested that a copy of the death certificate and a copy of the autopsy report, if applicable, be sent to the CRO. Any other source documents related to the death should also be provided to the CRO. If no source documents are available, the PI is required to describe the circumstances of the subject's death in written communication (e.g., letter, e-mail).

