13.2 Other Study-Specific Definitions

Device interference: Interaction of the EmStop System with the TAVR system that leads to:

- Inability to advance or manipulate the TAVR system, or
- Inability to deploy the TAVR system, or
- Inability to retrieve the TAVR system

Device procedural success: Successful insertion, deployment, positioning, and removal of the EmStop System in the absence of device interference.

Major adverse cardiac and cerebrovascular events (MACCE): All-cause mortality, all stroke (disabling and non-disabling) and transient ischemic attack (TIA), and acute kidney injury (AKI) Stage 2 or 3 (including renal replacement therapy). MACCE events will be adjudicated by the Medical Monitor using VARC-2 definitions [*Kappetein 2013*].

Montreal cognitive assessment (MoCA): A highly sensitive tool for early detection of mild cognitive impairment that was validated in 2000. [https://www.mocatest.org/]

National Institutes of Health Stroke Scale (NIHSS): A systematic assessment tool that provides a quantitative measure of stroke-related neurologic deficit. [https://www.nihstrokescale.org/]

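### AKI Stage 2 or 3 is a 72-hour endpoint component, but the one scheduled post-procedure renal draw may fall at any hour up to 72, so laboratory-defined cases can be missed

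*Combined protocol and SAP*

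**What the plan says.** Section 5.1 makes the following one of three components of the primary safety endpoint: "Acute kidney injury (AKI) Stage 2 or 3 (including renal replacement therapy) within 72 hours".

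The post-procedure renal measurement belongs to the pre-discharge visit. Under section 7.6 that visit is due "before discharge or 7 days post-op, whichever occurs first", with a specific limit for the blood work: "Pre-discharge labs will be collected within 72 hours post-procedure". Table 2 shows a single pre-discharge laboratory entry, and its footnote 7 repeats the limit. The renal analyte listed is GFR. After that, GFR is next scheduled at the 30-day visit (± 7 days), where it is the only laboratory test (Table 2, footnote 8).

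Events can also reach the endpoint through adverse event reporting. Section 11.2 states: "Collection of adverse events will start on the day of the procedure for enrolled subjects and will be assessed and reported throughout the study". Section 13.2 adds: "MACCE events will be adjudicated by the Medical Monitor using VARC-2 definitions".

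For the analysis, section 8.1 states: "The primary analysis will consist of all available data on all subjects enrolled". Section 8.3 makes the primary safety analysis descriptive. Section 8.9 leaves missing-data handling to a SAP whose detail is not reproduced in the document.

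**The concern.** The endpoint runs to 72 hours, while the renal measurement may stop much earlier. Section 7.6 gives the post-procedure MRI both an opening and a closing time (18 and 36 hours) but gives the blood draw only a closing time. It asks for no repeat draw and no sample near 72 hours. Because the draw belongs to the pre-discharge visit, early discharge brings it forward.

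A Stage 2 or 3 event defined by laboratory values can be found only if blood is taken while the abnormality is present. If the one scheduled sample comes before it, the protocol requires nothing further inside the window. A measurement at day 23 to 37 cannot show a change that came and went within three days.

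AKI is a listed device risk (section 10.3), and patients are excluded for renal failure only below an eGFR of 30 (section 6.5.3, item 8). The objective is to demonstrate safety (section 4.0), and the point estimates are meant to inform a pivotal study (section 8.8). Under-ascertainment here makes the device look safer, and most so in subjects discharged early.

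**Working it through.** The plan has no figure to reproduce. Its sample size of 15 is stated without power, effect size or event rate (section 8.8), and this point does not affect it. The check compares passages; the arithmetic only gives scale.

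**Step 1. Endpoint against schedule.**

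| Item | Timing | Source |
|---|---|---|
| AKI component | 0 to 72 h | Section 5.1 |
| Scheduled post-procedure GFR | Once, any time from 0 to 72 h | Section 7.6; Table 2, footnote 7 |
| Post-procedure MRI, for comparison | 18 to 36 h | Section 7.6; Table 2, footnote 6 |
| Next scheduled GFR | Day 23 to 37 (30 ± 7) | Section 7.7; Table 2, footnote 8 |

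The schedule guarantees one renal value in the window and does not guarantee where it falls.

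**Step 2. Share of the window elapsed at a draw t hours after the procedure: t/72.**

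- 6 h: 6/72 = 8%
- 18 h: 18/72 = 25%
- 24 h: 24/72 = 33%, leaving 72 − 24 = 48 h with no scheduled renal measurement
- 36 h: 36/72 = 50%
- 48 h: 48/72 = 67%

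All of these draws comply with section 7.6. The shares describe elapsed time. They would be detection rates only if onset were uniform over 72 hours and the abnormality persisted to the draw, and the documents support neither assumption.

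**Step 3. Effect of one missed case.** 1/15 = 6.7%. With exact (Clopper-Pearson) 95% intervals, which the plan does not call for and which are shown only for scale:

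- 1/15: 6.7% (0.2% to 31.9%)
- 0/15: 0% (0% to 21.8%)

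The AKI rate moves by 6.7 percentage points per missed case. MACCE moves by the same amount only if the subject has no other component.

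**Step 4. Chance of missing at least one case.** Let p be the true AKI Stage 2 or 3 rate and s the share of those cases that become detectable only after the draw. The documents give neither, so both are assumptions. P(at least one missed) = 1 − (1 − p·s)^15. For example, p = 5% and s = 0.50 gives 1 − 0.975^15 = 1 − 0.684 = 32%.

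| p | s = 0.25 | s = 0.50 | s = 0.75 |
|---|---|---|---|
| 2% | 7% | 14% | 20% |
| 5% | 17% | 32% | 44% |
| 10% | 32% | 54% | 69% |

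The expected number missed, 15·p·s, runs from 0.075 to 1.125. For given p and s these figures are upper limits, because adverse event reporting may recover some of the cases.

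**The case against.** The best defence is that the scheduled draw is not the only route to an AKI event. Adverse events are collected from the procedure day, and section 13.1 includes abnormal laboratory findings in the definition. Unscheduled-visit assessments are recorded (section 7.8). Endpoint and adverse event data are fully checked against source, with a search for unreported events (section 12.6), and the Medical Monitor adjudicates MACCE and may request source records. Extra draws are not prohibited. The MRI is itself a pre-discharge assessment at 18 to 36 hours, so a draw at 6 hours is unlikely to be forced by discharge. The study is a descriptive feasibility study without a success criterion.

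Most of this stands, and it limits the point. A reader might infer that nobody observes the subject after an early draw. The documents do not support that: clinical observation continues, and dialysis or overt renal failure would probably be reported. What is missing is scheduled laboratory ascertainment. The other routes do not replace it, because an abnormal value can be reported, verified or adjudicated only if a sample exists, and no section requires routine in-hospital renal values to be entered.

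A reader might also infer that the plan scores an early-draw subject as free of AKI. No such rule is written. It is the likely result of a descriptive count on available data, but it remains an inference while the SAP detail is unseen. A compliant early draw is not plainly missing data either, so a missing-data rule might not reach it.

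Finally, a reader might suspect the baseline value, since section 6.5.3 says "Diagnostic cardiac catheterization is permitted up until baseline MRI is" obtained. The documents do not show that catheterization is expected after the baseline labs. Any carried-over effect could push the AKI count either way, so this adds nothing to the point.

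**Conclusion.** The point holds as a gap in ascertainment. The protocol counts AKI Stage 2 or 3 to 72 hours but guarantees only one renal value, at an hour it does not fix. Laboratory-defined cases arising after an early draw can be missed, which biases the descriptive AKI and MACCE rates towards no event.

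The size per case is firm: 6.7 percentage points with 15 subjects, for MACCE provided the subject has no other component. The frequency is not known. The 7% to 69% range in Step 4 rests wholly on assumed rates and assumed shares of late detection, and the elapsed-time shares are illustration only. Sample size and power are not affected.

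The 72-hour limit is itself not settled. Section 13.2 defines MACCE with no time limit on AKI and adds TIA, which section 5.1 leaves out and section 5.3 lists as a secondary endpoint. Without the limit, the stretch with no scheduled renal value would extend from the draw to day 23 at the earliest, so that reading widens the gap.

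**What to change.** 1. **Timing.** In section 7.6 and Table 2, footnote 7, give the draw a lower limit: for example, no earlier than the 18-hour opening of the MRI window, and as late as possible before the earlier of discharge and 72 hours. The lower limit alone is not enough, since at 18 hours only a quarter of the window has passed.
2. **Capture and staging.** Enter on the eCRF every serum creatinine and GFR value obtained in routine care up to 72 hours, with its time. Name the measure used for staging, and stage AKI on the worst value.
3. **Reporting.** Give the hour of each subject's last renal value. Keep all enrolled subjects in the primary denominator, list those not sampled late in the window as incompletely assessed for AKI, and add a sensitivity summary restricted to those who were. State in the SAP, with a reason and before the data are reviewed, which hour counts as late; the documents give no basis for choosing one here.
4. **Definition.** Reconcile sections 5.1 and 13.2 on the 72-hour limit and on TIA.

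The cost is protocol and SAP wording and a few eCRF fields, with no added visit or procedure. The small downside is that some subjects will be shown as incompletely assessed. With 15 subjects the restricted summary may be small, so it should supplement the primary count and not replace it.

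### No NIHSS is scheduled after discharge or day 7, so a mild, unreported stroke before day 30 can be missed in a primary endpoint that counts all stroke

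*Combined protocol and SAP*

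**What the plan says.** Protocol section 5.1 sets the horizon: "The primary safety endpoint for the study is the occurrence of MACCE at 30 days". One of its components is "All stroke (disabling and non-disabling", so a minor stroke counts as much as a major one.

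NIHSS is listed at baseline (section 7.4) and at pre-discharge (section 7.6, "National Institute of Health Stroke Scale (NIHSS"). On the timing of the second, section 7.6 states that "the following assessments will be performed before discharge or 7 days post-op, whichever occurs first".

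The next and last scheduled contact is "7.7 30-Day [± 7 days] Follow-up Visit". Its list has adverse event assessment, antithrombotic medication, GFR, "Montreal cognitive assessment (MoCA" and "Modified Rankin Scale (mRS". NIHSS is not on it. Table 2 shows the same pattern and marks the 30-day contact as a clinic visit. Post-procedure MRI is done once, at 18-36 hours.

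Section 11.2 says that adverse events "will be assessed and reported throughout the study".

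**The concern.** The endpoint runs to day 30, but the only scheduled instrument that scores a stroke-related neurological deficit stops at discharge or day 7. Section 13.2 describes NIHSS as a measure of exactly that deficit, and describes MoCA as a tool for mild cognitive impairment. The mRS grades overall disability. A slight focal deficit need not move either of the two scales used at day 30, and a non-disabling stroke is the kind that a disability scale is least suited to show.

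The error has one direction. An unrecognised stroke can only lower the observed MACCE rate. The study aims to demonstrate safety (section 4.0), lists reduced stroke risk as its one potential benefit (section 10.1), and is to supply event frequencies for a pivotal design (section 8.8). A low count from incomplete ascertainment would carry over into that design.

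**Working it through.** **Step 1. Schedule against endpoint** (sections 7.4 to 7.7 and Table 2, which agree)

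| Visit | NIHSS | MRI | mRS | MoCA | AE assessment |
|---|---|---|---|---|---|
| Baseline | yes | yes, within 14 days before | yes | yes | no |
| Procedure | no | no | no | no | yes |
| Pre-discharge (by day 7) | yes | yes, 18-36 hours | no | no | yes |
| Day 30 ± 7, clinic | no | no | yes | yes | yes |

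The section lists and the table match, so the blank at day 30 is not a damaged table cell. Section 7.8 only asks that assessments done at unscheduled visits be recorded. Section 7.9 does not specify the content of the early-withdrawal visit. No section requires an NIHSS when a stroke is suspected.

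**Step 2. What still detects a stroke after discharge.** There are four routes: the scheduled AE assessment at day 30 (section 7.7); continuous AE collection (section 11.2); full source verification of endpoint and AE data, with review for unreported events (section 12.6); and Medical Monitor adjudication by VARC-2 (section 13.2). A stroke that produces a complaint or a medical record has several ways in. What remains is a deficit that is mild, unreported, and without effect on mRS or MoCA.

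**Step 3. Size of one miss.** Input: N = 15 (section 8.8).

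- Change in observed rate = 1/N = 1/15 = 6.7 percentage points, if that subject has no other MACCE event.
- If that stroke would have been the only event in the study: 1/15 = 6.7% (exact 95% interval 0.2% to 31.9%) becomes 0/15 = 0% (0% to 21.8%).
- If it would have been the second: 2/15 = 13.3% (1.7% to 40.5%) becomes 1/15.

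**Step 4. Can the chance of a miss be derived?** Section 2.0 cites two rates: 4.1% stroke in the first 10 days, and 3.8% cerebrovascular events at 30 days.

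- 15 × 0.041 = 0.62 expected strokes in 10 days.
- 15 × 0.038 = 0.57 expected cerebrovascular events in 30 days.

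Neither is a rate for the period after the pre-discharge examination, and the second is not confined to stroke. Going further needs two assumptions that are not in the documents: the share s of events that fall after the last NIHSS, and the share m of those that escape the routes in Step 2. Expected misses = 15 × p × s × m, and P(at least one) = 1 − (1 − p × s × m)^15.

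- Low end (p = 0.038, s = 10%, m = 25%): 0.014 expected; P = 1.4%.
- High end (p = 0.041, s = 50%, m = 100%): 0.31 expected; P = 26.7%.

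The high end supposes that every late stroke escapes all existing routes, which is not credible given Step 2. The range shows only that the result depends on the assumptions.

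**The case against.** The case against is substantial, and most of it limits the point.

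- **Detection is scheduled.** A reader might infer that stroke detection after discharge depends on spontaneous reports. It does not: AE assessment is a listed item at the 30-day clinic visit and is backed by source verification. This stands, and it confines the gap to mild, unreported deficits.
- **Expected counts.** A reader might set one missed stroke against the 0.57 to 0.62 expected events and conclude that the whole expected count could vanish. Those figures cover early and late, disabling and non-disabling events, and the 0.57 is not strokes alone. The documents do not support the comparison.
- **Counting days.** A reader might also count the days without an NIHSS. Even at the day-7 limit, 30 − 7 = 23 days follow the last one, and an earlier discharge would leave more. The documents give no usual discharge day, risk is not shown to be even over the month, and one added NIHSS is a single time point rather than cover for those days.
- **Device relevance.** The filter is in place only during TAVR (section 3.2), and the first days have both NIHSS and diffusion MRI. Late strokes say less about the device. This stands, but section 5.1 counts them all the same.
- **No decision rule.** The analysis is descriptive, without a success criterion (sections 8.3 and 8.8), and the exact intervals for 0/15 and 1/15 overlap widely. This stands: neither power nor type I error is affected.
- **Case definition.** NIHSS is not the protocol's definition of stroke, and the Medical Monitor's guidelines are not among the documents. A worsened score should therefore prompt review and not count as an event by itself.

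**Conclusion.** The point holds in a narrow form. The protocol counts non-disabling stroke to day 30 but schedules no neurological deficit score after discharge or day 7, and no imaging after 36 hours. A mild, unreported focal deficit that leaves mRS and MoCA unchanged can be missed, and the bias is downward.

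The size of one miss is firm: 6.7 percentage points at N = 15, provided that the subject has no other MACCE event. The probability of a miss is not known and cannot be obtained from the documents. The conclusion also rests on the general property that mRS and MoCA can be insensitive to a slight focal deficit. This is a cheap improvement to the ascertainment of one primary endpoint component, not a flaw that invalidates the study.

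**What to change.** Add NIHSS to the 30-day column of Table 2, to the list in section 7.7, and to the early-withdrawal visit in section 7.9. State that a worsening from the baseline or pre-discharge score is referred to the Medical Monitor for adjudication by VARC-2.

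The cost is a few minutes per subject, in at most 15 subjects, at a clinic visit that already takes place and with a scale the sites already use. Sample size, analysis and treatment do not change.

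The gain is limited. The examination finds only deficits that persist to the visit. Because the window opens at day 23 (30 − 7), an early visit leaves up to 7 endpoint days after it, for which AE reporting remains the only route.
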